- ECOG performance status.

Statistical Methods

Sample Size

Approximately 1000 patients will be randomized in a 4:4:1:1 ratio to receive treatment with one of the following 4 arms:

Arm A: Oral rucaparib + IV nivolumab (n = 400),

Arm B: Oral rucaparib + IV placebo (n = 400),

Arm C: Oral placebo + IV nivolumab (n = 100), or

Arm D: Oral placebo + IV placebo (n = 100).

The randomization is stratified by the following factors; HRD classification (tBRCA, non-tBRCA LOH^{high}, non-tBRCA LOH^{low}, and non-tBRCA LOH^{unknown}), disease status (no residual disease vs. residual disease), and timing of surgery (primary surgery vs. interval debulking).

Two separate comparisons of the treatment arms will be evaluated independently, and at different timepoints based on the maturity of the parts of the study:

- Monotherapy: Arm B (oral rucaparib + IV placebo) vs Arm D (placebo [oral and IV])
- Combination: Arm A (oral rucaparib + IV nivolumab) vs Arm B (oral rucaparib + IV placebo)

The level of statistical significance will be split into 2 so that each of the above comparisons will be made independently at a one-sided 0.0125 (two-sided 0.025) significance level.

The sample size is based on setting the power for each of the 2 independent treatment comparisons at 90% power. The power assumptions are based on the median PFS for patients in Arm A (oral rucaparib + IV nivolumab) from the total patient population (ie, the ITT population inclusive of both tBRCA and non-tBRCA subgroups) is expected to be approximately 28 months while the median PFS for patients in Arm B (rucaparib monotherapy [oral rucaparib + IV placebo]) is expected to be about 20 months.

The following table provides the sample size and power for the combination treatment comparison of Arm A (oral rucaparib + IV nivolumab) to Arm B (rucaparib monotherapy) for the ITT Population.

Group	Hazard Ratio	Cumulative N (4:4)	Number of Events	Median PFS (months)	Power	One-sided Alpha
ITT	0.725	800 (400:400)	600	20 vs 28	90%	0.0125

Abbreviations: ITT = intent-to-treat; PFS = progression free survival.

The following table provides the sample size and power for the monotherapy treatment comparison of Arm B (rucaparib monotherapy) to Arm D (placebo) for the HRD and ITT sub/populations.

Group	Hazard Ratio	Cumulative N (4:1)	Number of Events	Median PFS (months)	Power	One-sided Alpha
HRD	0.45	205 (164:41)	123	12 vs 26.7	90%	0.0125
ITT	0.60	500 (400:100)	300	12 vs 20	90%	0.0125

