1	ITT	500 (400:100)	340	HR 0.65 12 vs 17 months	90%	0.008	
Amendment 2	HRD	205 (164:41)	123	HR 0.45 ⁸² 12 vs 26.7 months	90%	0.0125	
	ITT	500 (400:100)	300	HR 0.60 ⁸² 12 vs 20 months	90%	0.0125	

Abbreviations: HR = hazard ratio; HRD = homologous recombination deficiency (tBRCA + non-tBRCA LOH high); ITT = intent-to-treat, IV = intravenous; PFS = progression-free survival.

The power assumption for the combination treatment comparison is still set at 90% power for both HRD and ITT sub/populations as per original protocol, as shown in the table below.

The following table provides the sample size and power for the clinically relevant comparison between Arm A (oral rucaparib + IV nivolumab) and Arm B (oral rucaparib + IV placebo) within the HRD and ITT sub/populations.

			` '	parib + IV nivolumab) vs Arm	B (oral
rucaparib + IV p	olacebo), ra	andomization allo	cation 4:4			
Protocol	Group	Cumulative N	Number of	HR	Power	One-side

Protocol Version	Group	Cumulative N (4:4)	Number of Events	HR Median PFS	Power	One-sided Alpha
Original	HRD	540 (270:270)	400	HR 0.67 25 vs 37 months	90%	0.008
Protocol and Amendment 1	ITT	800 (400:400)	600	HR 0.725 17 vs 24 months	90%	0.008
Amendment 2	HRD	380 (190:190)	285	HR 0.67 26.7 vs 39.9 months	90%	0. 0125
	ITT	800 (400:400)	600	HR 0.725 20 vs 28 months	90%	0. 0125

Abbreviations: HR = hazard ratio; HRD = homologous recombination deficiency (tBRCA + non-tBRCA LOH^{high}); ITT = intent-to-treat, IV = intravenous; PFS = progression-free survival.

9.2.3 Sample Size Assumptions as of Implementation of Protocol Amendment 3

The sample size and power assumptions are not changing in Amendment 3. The changes to remove the HRD sub-population from the primary and key secondary endpoints for the combination treatment comparison will not affect the current sample size design nor power of this study, due to the combination treatment comparison already being set at 90% power for the ITT Population, as shown in Section 9.2.2 and summarized in the table below.

Combination Treatment Comparison: Arm A (oral rucaparib + IV nivolumab) vs Arm B (oral
rucaparib + IV placebo), randomization allocation 4:4

Protocol Version	Group	Cumulative N (4:4)	Number of Events	HR Median PFS	Power	One-sided Alpha
Amendment 2	HRD	380 (190:190)	285	HR 0.67 26.7 vs 39.9 months	90%	0. 0125
Amenument 2	ITT	800 (400:400)	600	HR 0.725 20 vs 28 months	90%	0. 0125
Amendment 3	ITT	800 (400:400)	600	HR 0.725 20 vs 28 months	90%	0. 0125

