## 2.4 ATHENA-COMBO Sample Size

The median PFS for patients in Arm A (rucaparib+nivolumab) from all randomized patients (ie, the ITT Population inclusive of both tBRCA and non-tBRCA subgroups) is expected to

Confidential 16 of 52

be approximately 28 months while the median PFS for patients in Arm B (rucaparib monotherapy [rucaparib + IV placebo]) is expected to be about 20 months.

The following table provides the sample size and power for the ATHENA-COMBO comparison of Arm A (rucaparib+nivolumab) to Arm B (rucaparib monotherapy) in the ITT Population.

Group	Hazard Ratio	Cumulative N (4:1)	Number of Events	Median PFS (months)	Power	One- sided Alpha
ITT	0.725	800 (400:400)	600	20 vs 28	90%	0.0125

Abbreviations: ITT =intent-to-treat, PFS = progression-free survival Assumed accrual duration is 24 months.

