#### The IDMC will:

- Review safety and efficacy of rucaparib and nivolumab compared with placebo, as well as the rucaparib + nivolumab combination compared to monotherapy to ensure the study is beneficial to patients.
- Ensure the study is conducted in a high-quality manner.
- Monitor the size of the tBRCA subgroup.

Following data review, the IDMC will recommend continuation, revision, or termination of the study and/or continuing or halting enrollment into a particular subgroup. No formal efficacy interim analyses for early stopping are planned for this study.

Confidential 17 of 52

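### The ATHENA-COMBO sample-size row states 90% power, but its own inputs give about 95%

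*Protocol*

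**What the plan says.** The synopsis (Statistical Methods, Sample Size) says "The sample size is based on setting the power for each of the 2 independent treatment comparisons at 90% power", and that "each of the above comparisons will be made independently at a one-sided 0.0125 (two-sided 0.025) significance level". The combination row of its table reads "ITT 0.725 800 (400:400) 600 20 vs 28 90% 0.0125": hazard ratio, patients per arm, events, median PFS in months, power and one-sided alpha.

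The same row appears in Protocol 9.2.2 and 9.2.3 ("HR 0.725 20 vs 28 months", 600 events, 90%, 0.0125). Section 9.2.3 argues that dropping the HRD subpopulation from the combination testing leaves the study's power unaffected, "due to the combination treatment comparison already being set at 90% power for the ITT Population".

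ATHENA-COMBO SAP 2.4 repeats the figures, introduced by "The following table provides the sample size and power for the ATHENA-COMBO comparison of Arm A". Its patient-number column is labelled 4:1, although the cell beneath shows 400:400 and the protocol's tables say 4:4. SAP 2.5 states "No formal efficacy interim analyses for early stopping are planned for this study".

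**The concern.** For a log-rank test under proportional hazards, the number of events, the hazard ratio, the allocation and alpha together fix the power. The row gives all four and then a power that does not follow from them.

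The direction is safe, since the comparison has more power than stated. What is lost is an accurate account of the design. At the assumed effect the chance of missing it is about half of what the row implies, which bears on how informative a non-significant result would be. Nor is the reader told that 600 events give 90% power against a weaker effect, 0.75. The row therefore leaves open which was intended: 90% at 0.725 with fewer events, or 600 events with a different hazard ratio or power.

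**Working it through.** **Inputs** (Protocol synopsis; repeated in Protocol 9.2.3 and COMBO SAP 2.4): 600 events; HR 0.725; allocation 1:1; one-sided alpha 0.0125, so z = 2.2414. For 90% power, z = 1.2816. There is no efficacy interim on invPFS, so the full alpha is available at the one analysis.

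**Does the formula reproduce the plan's other rows?** Schoenfeld: power = Φ(√(D·p·(1−p))·|ln HR| − z). With 4:1 allocation, p(1−p) = 0.16.

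- Monotherapy HRD (123 events, HR 0.45): √19.68 × 0.7985 − 2.2414 = 1.301, power 90.3%.
- Monotherapy ITT (300 events, HR 0.60): √48 × 0.5108 − 2.2414 = 1.298, power 90.3%.

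Both agree with the stated 90%.

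**The combination row.** With 1:1 allocation, p(1−p) = 0.25.

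- Schoenfeld: √150 × 0.3216 − 2.2414 = 1.697, power 95.5%.
- Freedman: √600 × (0.275/1.725) − 2.2414 = 1.664, power 95.2%.
- Simulated log-rank test (exponential PFS, Arm B median 20 months, uniform 24-month accrual as in SAP 2.4, cut at the 600th event, unstratified, no drop-out): 95.2% in 10,000 trials and 95.6% in a separate run of 4,000.

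**In reverse.**

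- Events for 90% at HR 0.725, Schoenfeld: (2.2414 + 1.2816)² / (0.25 × 0.3216²) = 480.05, so 481. Freedman gives 488.3, so 489. The row has 111 to 119 more.
- HR with 90% power at 600 events: exp(−3.523/√150) = 0.750 (Freedman 0.749). Power at HR 0.75 is 90.0% (Schoenfeld), 89.6% (Freedman) or 90.5% (simulation).

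**Other readings of the row (Schoenfeld unless noted).**

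| Reading | Power at 600 events |
|---|---|
| HR rounded, anywhere from 0.7245 to 0.7255 (both formulas) | 95.1% to 95.6% |
| HR taken from the medians, 20/28 = 0.714 | 97.0% |
| 0.0125 read as two-sided | 92.5% |
| The superseded one-sided 0.008 | 93.7% |
| Allocation 4:1, as the SAP label says | 81.8% |

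None gives 90%. Drop-out changes when the 600th event occurs, not the power once it has occurred.

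**A check that needs no formula.** The comparison table in Protocol 9.2.2 shows HR 0.725, 600 events and 90% at one-sided 0.008, and again at 0.0125. With events, hazard ratio and allocation fixed, power must rise when alpha rises, so the same figure cannot be exact for both rows.

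**The case against.** The strongest reply is that 600 was chosen for data maturity and that 90% is a carried-over planning target. In the Amendment 2 tables both combination rows sit at 75% maturity (600/800 and 285/380) and both monotherapy rows at 60% (300/500 and 123/205). Protocol 9.2.2 does tie the monotherapy read-out to about 60% of events. Until Amendment 3 the HRD subpopulation was tested first in the combination hierarchy. With 285 events at HR 0.67 it had about 87% power, so it was the limiting row, and an ITT count at the same maturity would exceed what ITT alone needed. This is a plausible origin for the 600, but it is inferred from the tables. It explains the event count, not the 90% printed beside it, and the documents do not describe 90% as a minimum.

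Three further points have some force:

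- The 95% holds only if 600 events are observed. COMBO SAP section 1 speaks of a visit cut-off at maturity and does not name 600 as the trigger. At 500 events power would be √125 × 0.3216 − 2.2414 = 1.354, about 91%. The restated figure should therefore be tied to 600 events.
- A non-significant result would be read mainly from the estimated hazard ratio and its confidence interval, which SAP 10.1 requires. That limits the practical harm but does not make the stated power correct.
- Protocol 9.2.2 records the design as of Amendment 2, and under Protocol 10.7 a protocol change needs ethics approval and regulatory submission. A footnote there is enough. The current statements in the synopsis, 9.2.3 and SAP 2.4 are the ones to correct.

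The 4:1 label is a separate slip and does not explain the 90%.

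**Conclusion.** The concern holds. On its own inputs the ATHENA-COMBO ITT comparison has about 95% power (95.2% to 95.6% across two formulas and simulation), not 90%. Type II error is about 4.5% to 4.8%, not 10%. The synopsis sentence giving 90% for both comparisons is accurate for monotherapy and inaccurate for the combination.

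The result assumes proportional hazards, 600 observed events, 1:1 allocation and a single analysis at one-sided 0.0125. The calculations are for an unstratified test, whereas the planned test is stratified; any small loss from stratification was not quantified.

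The misstatement is conservative. It should be corrected because it concerns the only primary hypothesis of ATHENA-COMBO and Protocol 9.2.3 relies on the figure, but it does not threaten the validity of the trial.

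**What to change.** - In COMBO SAP 2.4, the protocol synopsis and the Amendment 3 row of Protocol 9.2.3, restate the row as 600 events, about 95% power at HR 0.725 (90% power at HR 0.75), and name the formula. Protocol 9.2.2 can take a footnote.
- Reword the synopsis sentence so that it no longer gives 90% for both comparisons.
- Change the column label in COMBO SAP 2.4 from 4:1 to 4:4.
- Optionally, footnote that 20 vs 28 months is rounded: HR 0.725 with a 20-month control median corresponds to 20/0.725 = 27.6 months.

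If the sponsor would rather keep 90% at HR 0.725 and change the event target, the new target must be a single number fixed before the COMBO comparison is unblinded.

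The recommended change is wording only. It alters no sample size, event target, alpha, analysis timing or conduct. The SAP correction can be made directly; the protocol text can wait for the next amendment.

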That is, for the monotherapy treatment comparison, the invPFS in the HRD subpopulation will be tested first at a one-sided 0.0125 significance level. If invPFS in the HRD subgroup is statistically significant, then invPFS will be tested in the ITT Population. If both the HRD and ITT sub/populations reach statistical significance for the primary endpoint, then the first secondary endpoint of OS will be tested at the one-sided 0.0125 significance level in the HRD and ITT sub/populations for that treatment comparison. If both the HRD and ITT sub/populations reach statistical significance, then testing will continue in an ordered step-down fashion to the last key secondary endpoint of ORR. Once statistical significance is not achieved for one test, the statistical significance will not be declared for all subsequent analyses in the ordered step-down procedure for the monotherapy treatment comparison.

Enrollment of tBRCA is much lower than originally anticipated in the sample size assumptions in the original protocol. Thus, the monotherapy treatment comparison will start with the HRD analysis population, then ITT Population for the step-down hierarchical testing. The tBRCA subgroup will be an exploratory endpoint for monotherapy treatment, in order to estimate the contribution within the HRD and ITT sub/populations.

For the combination treatment comparison, invPFS in the ITT Population will be tested first at a one-sided 0.0125 significance level. If invPFS is statistically significant, then the first secondary endpoint of OS will be tested at the one-sided 0.0125 significance level in the ITT Population and testing will continue in an ordered step-down fashion to the last key secondary endpoint of ORR. Once statistical significance is not achieved, the statistical significance will not be declared for subsequent analyses in the ordered step-down procedure for the combination comparison in the ITT Population. An exploratory endpoint evaluating efficacy within subgroups based on HRD, tBRCA, and PD-L1 for the combination treatment comparison will be evaluated.

Secondary Efficacy Endpoints

PFS as assessed by BICR review (bicrPFS) by RECIST will be tested as a stand-alone secondary endpoint, outside of the step-down procedure for multiplicity adjustment, due to

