#### Hypothesis:

H0: HR (Arm B/Arm D)  $\geq$  1. Ha: HR (Arm B/Arm D)  $\leq$  1.

In order to preserve the overall family-wise type 1 error rate between the ATHENA-MONO and the ATHENA-COMBO, the overall one-sided alpha of 0.025 is equally split in two between these comparisons, which means that all efficacy analyses will be tested at a one-sided 0.0125 significance level (two-sided p = 0.025) for all endpoints in ATHENA-MONO.

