## 3.4 Step-down Procedure of Primary and Secondary Endpoints

[figure not shown]
In order to preserve the overall Type 1 error rate, while testing the primary and secondary endpoints for ATHENA-MONO, a hierarchical step-down procedure has been specified. Statistical significance will only be declared for any of the endpoints if the previous endpoints are also statistically significant at the significance level of two-sided 0.025. The step-down procedure is outlined in Figure 2.

The primary endpoint of invPFS and key secondary endpoints of OS and ORR will be tested among the HRD Population first and then the ITT Population using a one-sided alpha of 0.0125 (two-sided alpha = 0.025).

That is, the invPFS in the HRD Population will be tested first at a one-sided 0.0125 significance level. If invPFS in the HRD Population is statistically significant then invPFS will be tested in the ITT Population. If both the HRD and ITT Populations reach statistical significance for the primary endpoint, then the first secondary endpoint of OS will be tested at the one-sided 0.0125 significance level in the HRD and ITT Populations for that treatment comparison and testing will continue to the last key secondary endpoint of ORR. Once statistical significance is not achieved for one test, the statistical significance will not be declared for all subsequent analyses in the ordered step-down procedure for the comparisons of the rucaparib arm to placebo.

The bicrPFS will be evaluated as a stand-alone secondary endpoint and is not part of the hierarchical step down. The bicrPFS will be used as a supportive analysis to the primary endpoint. The secondary endpoint of DOR will also be evaluated as a stand-alone secondary endpoint and is not part of the hierarchical step down.

Figure 2 Ordered Step-down Procedure for ATHENA-MONO

Abbreviations: HRD = homologous recombination deficient; invPFS = progression-free survival as assessed by investigator; ITT = intent-to-treat, ORR = objective response rate; OS = overall survival.

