The stratified log-rank test of invPFS between the randomized treatment groups together with a graphical presentation of unstratified invPFS distributions, median invPFS with 95% CI, and event rates will be presented. Furthermore, the probability of being progression free at 6, 12, 18 and 24 months will be summarized by treatment group by using the Kaplan-Meier estimates, both unstratified and stratified, at each time point with 95% CIs using a log-log distribution.

In addition, the primary endpoint will also be analyzed using the stratified Cox proportional hazards model, presenting the hazard ratio with 95% confidence interval between the randomized treatment groups. The stratified log-rank test will be the official test used for the hierarchical testing outlined in Section 3.4.

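### At the planned 4:1 sizes, the monotherapy HRD gate test would have a benefit-direction false-positive rate of about 0.017, not the stated one-sided 0.0125

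*Protocol*

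**What the plan says.** The protocol synopsis (Sample Size) sets the allocation: "Approximately 1000 patients will be randomized in a 4:4:1:1 ratio". Arm B to Arm D is therefore 4:1. It also states that "each of the above comparisons will be made independently at a one-sided 0.0125 (two-sided 0.025) significance level". The monotherapy power table gives, for HRD, "205 (164:41) 123 12 vs 26.7" at HR 0.45 and, for ITT, "500 (400:100) 300 12 vs 20" at HR 0.60, each with 90% power.

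On order, the protocol says "the invPFS in the HRD subpopulation will be tested first at a one-sided 0.0125 significance level". ITT invPFS follows only if HRD succeeds, then OS, then ORR. The ATHENA-MONO SAP (3.3) says that "the overall one-sided alpha of 0.025 is equally split in two between these comparisons", and frames the hypothesis one-sidedly as HR (B/D) of 1 or more against an alternative that favours rucaparib. Section 3.4 introduces the step-down with "In order to preserve the overall Type 1 error rate, while testing the primary and secondary endpoints for ATHENA-MONO". Section 10.1 adds: "The stratified log-rank test will be the official test used for the hierarchical testing outlined in Section 3.4". Section 10.2.2 makes the stratified log-rank official for OS too.

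Sections 3 and 3.4 of the same SAP also express the threshold as two-sided 0.025. Neither document gives a permutation or exact reference distribution, or a small-sample correction, for the Arm B vs D log-rank test. The Firth correction in the ATHENA-COMBO SAP concerns the Cox model for the 1:1 comparison.

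**The concern.** The log-rank Z is close to standard normal when arms are of similar size. With four patients in one arm for each one in the other, it is skewed for two reasons. Each event contributes roughly a Bernoulli term with success probability 0.8, which has negative skew. The variance estimate also falls when the small arm happens to fail early. Both push probability into the tail that favours the large arm, which here is rucaparib.

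The claims are one-sided in substance: only superiority of rucaparib would be claimed. An error shifted from the harm tail to the benefit tail raises the chance of a false claim even though the two-sided total looks right. The HRD test has 41 controls and is the entrance to the whole monotherapy hierarchy. The same statistic is later official for OS. If rucaparib improves PFS but not OS, the HRD OS test becomes the first true null in the sequence, and its own benefit-tail rate is then the one that matters.

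**Working it through.** **Inputs.** Sizes, events, hazard ratios, medians and alpha come from the synopsis tables. Strata come from the randomisation factors: 2 × 2 × 2 = 8 in HRD and 4 × 2 × 2 = 16 in ITT. Scans are every 12 weeks. Accrual is taken as 24 months, stated in the ATHENA-COMBO SAP (2.4) for the same trial. Uniform accrual, exponential PFS and stratum sizes are assumptions.

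**The plan's own power.** Schoenfeld: power = Φ(√(D × 0.8 × 0.2) × |ln HR| − z), with z = 2.2414 for one-sided 0.0125.

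- HRD: √(123 × 0.16) × 0.7985 = 3.542; 3.542 − 2.241 = 1.301; Φ = 90.3%.
- ITT: √(300 × 0.16) × 0.5108 = 3.539; 3.539 − 2.241 = 1.298; Φ = 90.3%.

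Both match the stated 90%. The required events come to 122 and 298 against 123 and 300.

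**Analytic check on the tail.** A Bernoulli(0.8) term has skewness (1 − 1.6)/√0.16 = −1.5. Over D events the score has skewness −1.5/√D, which is −0.135 (HRD) and −0.087 (ITT). The Edgeworth tail is 0.0125 + (|skewness|/6)(z² − 1)φ(z), with z² − 1 = 4.024 and φ(z) = 0.0324.

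- HRD: 0.0125 + 0.0225 × 4.024 × 0.0324 = 0.0154.
- ITT: 0.0125 + 0.0144 × 4.024 × 0.0324 = 0.0144.

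This leaves out the variance effect, so simulation should give more.

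**Simulation under HR = 1**, event-driven cut-off, Z referred to the normal at ±2.2414:

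| Setting | Replicates | Benefit tail | Harm tail |
|---|---|---|---|
| HRD 164:41, 123 events, unstratified | 1,000,000 | 0.0174 | 0.0092 |
| HRD, 8 strata, blocked 4:1 (two hazard patterns) | 300,000 each | 0.0168, 0.0172 | 0.0093, 0.0091 |
| HRD, 12-week tied scan times | 120,000 | 0.0163 | 0.0099 |
| HRD, 100 events | 300,000 | 0.0174 | 0.0089 |
| HRD, 145 events | 300,000 | 0.0176 | 0.0096 |
| ITT 400:100, 300 events, unstratified | 1,000,000 | 0.0154 | 0.0104 |
| ITT, 16 uneven strata | 300,000 | 0.0152 | 0.0107 |

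The Monte Carlo standard error is about 0.0001 for the million-run rows. Varying the null median (12, 20, 26.7 months) and accrual (6, 24 months) kept HRD between 0.0165 and 0.0178. A 1:1 control with 123 events gave 0.0120 to 0.0127, so the excess comes from the allocation. The two-sided HRD total is 0.0174 + 0.0092 = 0.0266.

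**Size of the excess.** For HRD, 0.0163/0.0125 = 1.30 and 0.0174/0.0125 = 1.39. The trial-wide bound is 0.017 + 0.0125 = 0.0295.

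**Cut-offs that hold 0.0125.** About Z = −2.37 to −2.38 in HRD (nominal p about 0.009) and −2.33 in ITT (nominal p about 0.0098).

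**Power at those cut-offs.** Simulation under the plan's alternatives gives 93.0% to 93.4% (HRD) and 92.1% to 92.6% (ITT). Schoenfeld's formula with the same cut-offs would give Φ(3.542 − 2.37) = 88.0% and Φ(3.539 − 2.33) = 88.7%. That formula is itself a normal approximation with a fixed 4:1 risk set. The statement that 90% is still met therefore rests on the simulation, not on the formula.

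**The case against.** Several points on the other side are sound and limit the claim.

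- **A two-sided level is also stated, and it roughly holds.** A reader might infer that the test simply fails its significance level or that the documents contradict themselves. They do not. Only the one-sided level, which the plan also states, is exceeded. The Type 1 error sentence in MONO SAP 3.4 introduces the multiplicity procedure and does not promise finite-sample exactness.
- **The ITT figure is not an error rate of the procedure.** A reader might infer a false-positive rate of about 0.015 for the ITT claim. That holds only for the ITT test taken alone. In the step-down it is reached only after HRD succeeds. In a nested simulation under the global null (60,000 runs) both tests rejected in 0.0038 of runs, well below 0.0125.
- **The invPFS tests are done.** The ATHENA-COMBO SAP (2.3, 3.5) records a 23 March 2022 data cut-off and unblinding of Arms B and D. MONO SAP 3.5 plans no further invPFS analysis unless authorities ask. The gate can no longer be re-specified. Any change for OS also comes after an unblinding at which interim OS was to be summarised.
- **The log-rank test was requested by the regulator** (Amendment 5 entry, COMBO SAP Table 2), and MONO SAP v2.0 moved multiplicity testing from Cox to log-rank. A remedy should not undo this.
- **The sizes are planning figures.** Amendment 2 elsewhere assumes 190 HRD patients in Arm B. With 190:48 the rate is 0.0170, so the effect persists.

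What remains is a one-directional excess of about 0.0045. It changes a decision only if a one-sided p falls between about 0.009 and 0.0125.

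**Conclusion.** The point holds in this form. At the planned sizes, the 4:1 stratified log-rank test referred to the normal distribution would have a benefit-direction false-positive rate of about 0.017 for the HRD gate against a stated one-sided 0.0125. Because HRD invPFS is first in the sequence, that is the monotherapy family's rate under the global null, and the trial-wide one-sided bound becomes about 0.0295 rather than 0.025. The 1:1 combination test is not affected.

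This is a finite-sample property of an approximation. It rests on 164:41 patients with 123 events, exponential PFS and uniform accrual. Stratification, ties, event counts from 100 to 145, and different medians and accrual lengths left the rate between 0.0163 and 0.0178. For OS the documents give only 70% of deaths. If that is read as 70% of 205 patients (about 143 events), the rate was 0.0164 to 0.0171.

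A reader might go further and infer that the monotherapy invPFS conclusion is unsafe. The documents do not support that: they report no result, and a p-value well below 0.009 would make the issue moot for that test.

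**What to change.** Keep the stratified log-rank as the official statistic for Arm B vs Arm D, but take its one-sided p-value from the re-randomisation distribution: permute treatment labels 4:1 within the randomisation strata, for example 100,000 draws, and compare with 0.0125. Specify this in MONO SAP 3.4 and 10.2.2 for the final OS tests in HRD and ITT. Report the same p-value beside the invPFS tests already performed, as supportive information only.

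Do not substitute the Cox likelihood-ratio test. It held about 0.013 in simulation, but it would move the multiplicity test back off the log-rank. A Cox Wald p-value would not cure the problem (0.0163 HRD, 0.0150 ITT).

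The cost is a short SAP addition and a short program, with no change to data, sample size or official statistic. Because Arms B and D are already unblinded, the amendment should be dated and justified as such. At these sizes it makes the benefit-direction p-value slightly less favourable to rucaparib, so it cannot reasonably be read as seeking a positive result. In the invPFS design, simulated power at the corrected cut-offs is about 93% (HRD) and 92% (ITT). The documents state no power for OS.
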